## **2. OBJECTIVES AND ENDPOINTS**

This study will evaluate pharmacokinetics, pharmacodynamics and safety of etrolizumab in pediatric patients of 4 to  $<18$  years of age with moderate to severe UC or with moderate to severe CD.

This study will consist of multiple phases; a randomized treatment phase, followed by an OLE phase, and then a PML-monitoring phase. The objective of the 24-week randomized treatment phase is to evaluate the pharmacokinetics, pharmacodynamics, safety, and tolerability of etrolizumab in pediatric patients from 4 to  $<18$  years of age with moderately to severe UC or moderate to severe CD. The objective of the 312-week (6-year) OLE phase is to assess the long-term safety and efficacy of etrolizumab in pediatric patients from the randomized treatment phase. The objective of the 104-week PML safety-monitoring phase (*that includes the 12-week safety follow-up period after completion or early discontinuation from the OLE*) is to assess safety with focus on the occurrence of PML in patients who are no longer on etrolizumab.

Specific objectives and corresponding endpoints for the study are outlined below.

**Table 1 Objectives and Corresponding Endpoints for the Randomized Treatment Phase**

Primary Objective	Corresponding Endpoints

 
To evaluate the pharmacokinetics and pharmacodynamics of etrolizumab in a pediatric IBD patient population
 
	
 
PK parameters: <math>C_{max}</math>, <math>AUC_{tau}</math>, <math>t_{1/2}</math>, <math>C_{trough}</math>
 
PD parameters: <math>\beta 7</math> receptor occupancy by flow cytometry on peripheral blood lymphocytes
 

Safety Objective	Corresponding Endpoints

 
To evaluate the overall safety and tolerability of etrolizumab in pediatric population
 
	
 
Incidence and severity of infection-related adverse events
 
Incidence of immunogenic responses (ADAs)
 
Incidence and severity of hypersensitivity reaction events
 

Exploratory Objectives	Corresponding Endpoints

 
To evaluate additional pharmacodynamic biomarkers of etrolizumab
 
To evaluate clinical disease biomarkers with etrolizumab treatment
 
To evaluate the clinical efficacy of etrolizumab
 
	
 
Changes in serum MAdCAM-1
 
Changes in serum CRP and fecal calprotectin
 
Clinical response at Week 16, as assessed by the PUCAI (UC) and PCDAI (CD)
 

ADA=anti-drug antibody;  $AUC_{tau}$ =area under the concentration–time curve within a dosing interval; CD=Crohn's disease;  $C_{max}$ =maximum concentration observed; CRP=C-reactive protein;  $C_{trough}$ =steady-state concentration at the end of a dosing interval; MAdCAM-1=mucosal vascular addressin cell adhesion molecule-1; PD=pharmacodynamic; PK=pharmacokinetic; PCDAI=Pediatric Crohn's Disease Activity Index; PUCAI=Pediatric Ulcerative Colitis Activity Index;  $t_{1/2}$ =elimination half-life.

**Table 2 Objectives and Corresponding Endpoints for the Open-label Extension Phase**

Safety Objective	Corresponding Endpoints

 
To evaluate long-term safety of etrolizumab in pediatric population
 
	
 
Incidence and severity of infection-related adverse events
 
Incidence and severity of malignancies
 
Incidence of ADAs to etrolizumab
 
Incidence and severity of hypersensitivity reactions
 

Efficacy Objective	Corresponding Endpoint

 
To evaluate long term efficacy of etrolizumab in pediatric population
 
	
 
Clinical response at Week 132, as assessed by the PUCAI (UC) and PCDAI (CD)
 

ADA=anti-drug antibody; CD=Crohn's disease; OLE=open-label extension; PCDAI=Pediatric Crohn's Disease Activity Index; PUCAI=Pediatric Ulcerative Colitis Activity Index; UC=ulcerative colitis.

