#### **4.1.1 Inclusion Criteria**

Patients must meet the following criteria for study entry:

- Signed Informed Consent Form by parent or legal guardian
- Age of 4 years to  $<18$  years at the time of signing the Informed Consent Form
- Ability to comply with the study protocol, in the investigator's judgment
- Weight of 13 kg or more

- Diagnosis of UC or CD confirmed by biopsy and established for  $\geq 3$  months (i.e., after first diagnosis by a physician according to American College of Gastroenterology [ACG] guidelines) prior to screening
- Inadequate response, loss of response or intolerance to prior immunosuppressants and/or corticosteroid treatment and/or anti-TNF therapy
- For patients with UC: moderately to severely active UC as determined by an MCS of 6–12 with an endoscopic subscore  $\geq 2$  (within the last 12 months prior to screening) and a rectal bleeding subscore  $\geq 1$
- For patients with CD: moderately to severely active CD as determined by a Pediatric Crohn's Disease Activity Index (PCDAI) score of  $> 30$  at baseline
- Must meet the following surveillance colonoscopy requirements:
  - Document evidence of surveillance for dysplasia every 1 to 2 years, beginning approximately 7 to 10 years after their initial diagnosis
- For postpubertal females of childbearing potential: agreement to remain abstinent (refrain from heterosexual intercourse) or use acceptable contraceptive methods during the treatment period and for at least 24 weeks after the last dose of etrolizumab.

A female is considered to be of childbearing potential if she is postmenarcheal, has not reached a postmenopausal state ( $\geq 12$  continuous months of amenorrhea with no identified cause other than menopause), and has not undergone surgical sterilization (removal of ovaries and/or uterus).

Examples of acceptable contraceptive methods include bilateral tubal ligation, male sterilization, combined oral contraceptive pill or transdermal patch, spermicide and barrier [condoms], intrauterine device, implants for contraception, injections for contraception [with prolonged release], hormonal vaginal device (see [Appendix 6](#)).

The reliability of sexual abstinence should be evaluated in relation to the duration of the clinical trial and the preferred and usual lifestyle of the patient. Periodic abstinence (e.g., calendar, ovulation, symptothermal, or postovulation methods) and withdrawal are not acceptable methods of contraception.

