#### **Pediatric Crohn's Disease Activity Index (PCDAI)**

The PCDAI quantifies the signs and symptoms of patients with CD (see [Appendix 3](#)). The components of the PCDAI include patient- or caregiver-reported number of stools, abdominal pain, and general well-being; presence of extraintestinal manifestations; physical examination findings; height and weight, and hematocrit, erythrocyte sedimentation rate, and serum albumin over the past week (Hyams et al. 1991). Of these components, number of soft stools, abdominal pain, and general well-being are reported by patients (age  $\geq 7$  years) or caregivers of patients  $< 7$  years of age and the remaining components are completed by the physician. A numerical value is assigned to each response; responses are summed to a total score of 0-100, with a higher score indicating more severe disease. Please refer to [Appendix 3](#) for details.

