## **6.9 EXPLORATORY ANALYSES**

PUCAI/PCDAI response or remission rates will be summarized descriptively over time within each treatment group. Disease activity scores and subscores, fecal calprotectin levels and serum CRP levels and their change from baseline will also be summarized descriptively over time to assess the efficacy of etrolizumab in reducing signs and symptoms of disease and levels of inflammatory biomarkers.

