**Appendix 1c**  
**Schedule of Assessments: Open-Label Extension Phase (cont.)**

**Clinic Visits Week 96–Week 312, Unscheduled, and Early Withdrawal from Treatment (cont.)**

Assessments	Clinic Visit (± 7 days)	Clinic Visit (± 3 days)	Clinic Visit (± 3 days)	Clinic Visit (-14 days)	Unscheduled Visit c	Early Withdrawal from Treatment Visit d
	Weeks 96, 120, 144, 168, 192, 216, 240, 264, 288	Weeks 100, 104 , 112, 116, 124, 128, 136, 140, 148, 152, 160, 164, 172, 176, 184, 188, 196, 200, 208, 212, 220, 224, 232, 236, 244, 248, 256, 260, 268, 272, 280, 284, 292, 296, 304, 308	Weeks 108, 132, 156, 180, 204, 228, 252, 276, 300	Week 312		
Pregnancy test g	x	x	x	x	x	x
Hematology	x			x	x	x m
ESR h	x			x	x	x
Chemistry	x			x	x	x m
Hepatitis B DNA i	x			x	x	
Serum sample (CRP)	x				x c	x m
Etrolizumab PK sample (serum) j	x			x	x	
Anti-drug antibody sample (serum) j, k	x			x	x	x l, m
Etrolizumab administration	x	x	x	x	x	

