## Appendix 1c

### Schedule of Assessments: Open-Label Extension Phase (cont.)

ADA=anti-drug antibody; BP=blood pressure; CRP=c-reactive protein; ECG=electrocardiogram; eCRF=electronic case report form; ESR=erythrocyte sedimentation rate; GI=gastrointestinal; PD=pharmacodynamics; PK=pharmacokinetic; PCDAI=Pediatric Crohn's Disease Activity Index; PML=progressive multifocal leukoencephalopathy; PUCAI=Pediatric Ulcerative Colitis Activity Index.

- a Day 1 of Week 0.
- b Week 0 procedures and laboratory assessments that have been collected as part of the final visit for the safety follow-up period (within the treatment phase) do not need to be repeated, with the exception of ADAs, which must be recollected at Week 1 if the Week 0 visit occurs > 7 days after the final visit of the safety follow-up period.
- c Unscheduled visit represents a visit that is not as per the Schedule of Assessments and is required for an adverse event or for potential relapse assessment. All indicated assessments are NOT performed at each unscheduled visit. Assessments would be symptom driven (e.g., only perform PML neurologic examination if patient reports symptoms suspected to indicate PML). Assessments corresponding to items noted in this column should be recorded on the eCRF.
- d Denotes the early withdrawal from treatment visit for the open-label treatment period. To be performed within 30 days of last dose of study drug. Study drug is not administered at the Early Withdrawal from Treatment visit.
- e PML neurologic examination consists of the PML Subjective Checklist. Administer before other assessments, per [Appendix 7](#).
- f For children who are 6 years of age or younger, the parent or caregiver can respond to the questions on the patients behalf.
- g A urine test may be performed; however, if the urine test result is positive, a confirmatory serum test must be performed. Do not administer etrolizumab unless the serum pregnancy test result is negative. A urine pregnancy test is only required in female patients at Tanner Stage 2 or greater, or after onset of menarche. Test must be performed on fresh voided sample.
- h For patients with Crohn's disease only. Hematocrit, albumin, and erythrocyte sedimentation rate (ESR) will be collected to calculate the PCDAI score.

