### Pediatrics Crohn's Disease Activity Index (PCDAI)

ITEM	POINTS			
Abdominal pain				
None	0			
Mild (brief episodes, not interfering with activities)	5			
Moderate/severe (frequent or persistent, affecting with activities)	10			
Stools				
0-1 liquid stools, no blood	0			
2-5 liquid or up to 2 semi-formed with small blood	5			
Gross bleeding, >6 liquid stools or nocturnal diarrhoea	10			
Patient functioning, general well-being (Recall, 1 week)				
No limitation of activities, well	0			
Occasional difficulties in maintaining age appropriate activities, below par	5			
Frequent limitation of activities, very poor	10			
EXAMINATION				
Weight				
Weight gain or voluntary weight loss	0			
Involuntary weight loss 1-9%	5			
Weight loss >10%	10			
Height				
< 1 channel decrease (or height velocity > -SD)	0			
> 1<2 channel decrease (or height velocity < -1SD> -2SD)	5			
> 2 channel decrease (or height velocity < -2SD)	10			
Abdomen				
No tenderness, no mass	0			
Tenderness, or mass without tenderness	5			
Tenderness, involuntary guarding, definite mass	10			
Peri-rectal disease				
None, asymptomatic tags	0			
1-2 indolent fistula, scant drainage, tenderness of abscess	5			
Active fistula, drainage, tenderness or abscess	10			
Extra-intestinal manifestations				
Fever > 38.5 x 3 days in week, arthritis, uveitis, erythema nodosum, or pyoderma gangrenosum				
None	0			
One	5			
Two	10			
LABORATORY				
Hct (%)				
<10yrs	11-14 (male)	11-19 (female)	15-19 (male)	
> 33	> 35	> 34	> 37	0
28-33	30-34	29-33	32-36	2.5
< 28	< 30	< 29	< 32	5
ESR (mm/hr)				
< 20				0
20-50				2.5
> 50				5
Albumin (g/L)				
>35				0
31-34				5
<30				10

Disease activity

<10 – remission

10-27.5 – mild

30-37.5 – moderate

>40 – severe

TOTAL =

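### The only efficacy endpoint of the open-label extension, response at Week 132, falls on a visit with no PCDAI laboratory tests scheduled, so Crohn's disease patients have 8 of 11 components

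*Combined protocol and SAP*

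**What the plan says.** Section 2, Table 2 and the synopsis give the OLE efficacy objective a single endpoint: "Clinical response at Week 132, as assessed by the PUCAI (UC) and PCDAI (CD").

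In Appendix 1c, Week 132 belongs to the column headed "Weeks 108, 132, 156, 180, 204, 228, 252, 276, 300". The PUCAI/PCDAI row is ticked there, as are height, weight and the limited physical examination. The hematology, ESR and chemistry rows are blank. The neighbouring column, "Weeks 96, 120, 144, 168, 192, 216, 240, 264, 288", has the PCDAI and all three tests.

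Footnote h to Appendix 1c says why the tests are there: "Hematocrit, albumin, and erythrocyte sedimentation rate (ESR) will be collected to calculate the PCDAI score". Section 4.5.9 lists among the PCDAI components "hematocrit, erythrocyte sedimentation rate, and serum albumin over the past week". Appendix 3 scores all three.

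The only analysis text is Section 6.9: "PUCAI/PCDAI response or remission rates will be summarized descriptively over time within each treatment group". It has no rule for a PCDAI with missing items.

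**The concern.** The endpoint for a stated objective is placed at a visit where the schedule does not collect everything needed to compute it. For Crohn's disease patients the Week 132 score would then be missing, would borrow laboratory values 12 weeks away, or would be a truncated sum. The documents do not say which.

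The last option matters most. The baseline laboratory items are scheduled, so a full baseline would be compared with a partial follow-up score. Every omitted item can only lower the total, so the error runs towards apparent response.

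The stakes are limited. The endpoint is descriptive and not primary, and the PUCAI has no laboratory items, so ulcerative colitis patients are not affected. It is nevertheless the only efficacy measure named for a 312-week phase.

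**Working it through.** **1. Reproduce the PCDAI range (Section 4.5.9 states 0 to 100).** From Appendix 3:

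- Eight non-laboratory items at a maximum of 10 each: 8 × 10 = 80.
- Hematocrit 5 + ESR 5 + albumin 10 = 20.
- Total: 11 items, 80 + 20 = 100. This matches the stated range.

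**2. Read the Appendix 1c columns from Week 96.**

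| Row | 96, 120, 144 … 288 | 100, 104 … 308 | 108, 132 … 300 | 312 |
|---|---|---|---|---|
| PUCAI/PCDAI | x | – | x | x |
| Hematology (hematocrit) | x | – | – | x |
| ESR | x | – | – | x |
| Chemistry (albumin) | x | – | – | x |

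Hepatitis B DNA, CRP, PK and anti-drug antibody samples are also blank in the Week 108/132 column, so it has no scheduled blood draw from which the three results could be taken. At Week 132 the score has 11 − 3 = 8 items and a maximum of 100 − 20 = 80.

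**3. Compare with the other OLE visits that have a PCDAI.**

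- Weeks 4, 8, 12, 24, 36, 48, 60, 72, 84: 9 visits, all three tests ticked.
- Weeks 96 to 288 in the 96/120/144 column: 9 visits, all three ticked.
- Weeks 108 to 300 in the 108/132 column: 9 visits, none ticked.
- Week 312: 1 visit, all three ticked.

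The total is 9 + 9 + 9 + 1 = 28 visits, of which 9 + 9 + 1 = 19 have the tests and 9 do not. The 9 are exactly the column that holds the endpoint.

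**4. Check the week origin.** Counted from randomisation, Week 132 is OLE Week 132 − 24 = 108, in the same column. The gap to the nearest tests is 12 weeks either way: OLE Weeks 120 and 144 around 132, or 96 and 120 around 108. Section 4.5.9 ties the components to the past week.

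**5. Size the effect if undrawn items are scored zero (an assumption).** Crohn's disease entry in Section 4.1.1 requires "moderately to severely active CD as determined by a Pediatric Crohn's Disease Activity Index (PCDAI) score of" more than 30. Non-laboratory items move in steps of 5.

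- Laboratory items at maximum (20 points): the lowest eligible total is 15 + 20 = 35. Without them it is 15.
- Laboratory items at the intermediate level: 2.5 + 2.5 + 5 = 10 points. The lowest eligible total is 25 + 10 = 35. Without them it is 25.

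Appendix 3 places 35 in the band "30-37.5 – moderate" and both 15 and 25 in the mild band (10 to 27.5). The band changes although the patient has not.

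**6. Check the baseline.** In Appendix 1a the PCDAI, hematology and chemistry are on Day 1. ESR is at screening only, so it can be up to 35 days old, but it is drawn.

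**The case against.** The strongest reply is that footnote h, read with the PCDAI definition in Section 4.5.9, already requires the three tests whenever a PCDAI is done. A site might act on that. But at Weeks 4 and 8 the grid ticks hematology and chemistry explicitly under footnote h. When the schedule wants tests for the PCDAI, it marks the cell, and at Week 132 the cells are blank. At best, sites would differ in what they collect.

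Second, Section 6.9 summarises response over time, so complete scores at Weeks 120 and 144 would be reported anyway. This stands and limits the loss to one descriptive timepoint, in the Crohn's disease subset of about 24 enrolled patients who are still in an optional extension. It does not make the named endpoint computable.

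Third, the 20-point figure needs zero-scoring and the worst laboratory values, and no PCDAI response threshold is given. Both points are correct. The figure is an upper bound on the score, not an estimate of bias in the response rate. Completing the score would still leave PCDAI response undefined.

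Fourth, moving the timepoint also moves it for ulcerative colitis patients, needs approval under Section 9.6, and would be done in an open-label study whose sponsor is unblinded. These are real costs. They bear on which remedy to choose and do not remove the mismatch.

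**Conclusion.** The concern holds. As scheduled, the Crohn's disease part of the only named OLE efficacy endpoint rests on 8 of 11 PCDAI items, 80 of 100 points, whichever way Week 132 is counted. Nothing in the documents supplies the missing items or says how to score without them.

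Under the zero-scoring assumption the total could be understated by anything from 0 to 20 points, depending on the patient's true laboratory values. The effect on the response rate cannot be sized from the documents. The finding rests on reading the blank cells as not scheduled, which the consistent column alignment and the explicit marking at Weeks 4 and 8 support. It should be fixed, but it does not threaten the primary PK and PD objective or the safety conclusions.

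**What to change.** **Preferred:** in Table 2 and the synopsis, move the endpoint to Week 120 or Week 144 and state the week origin. The PCDAI and all three tests coincide there under either count: study Weeks 120 and 144 are OLE Weeks 120 − 24 = 96 and 144 − 24 = 120, both in the column with the tests. This restores 11 of 11 items with no new sample or visit. The cost is the wording change, taken through the amendment process of Section 9.6. The timepoint also shifts for ulcerative colitis. Because the study is open-label, the amendment should give the schedule mismatch as its reason.

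**Alternative:** keep Week 132 and tick hematology, ESR and chemistry there under footnote h for Crohn's disease patients only. This costs one added venipuncture per such patient, because that column has no scheduled draw. It must be checked against the blood-volume limits in Section 4.5.6, and it cannot help a patient who has already passed the visit.

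Under either option, Section 6.9 should say how a PCDAI without its laboratory items is handled, since the other visits in that column stay incomplete in the over-time summaries. It should also define PCDAI response.

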**Table 3 Objectives and Corresponding Endpoints for the Progressive Multifocal Leukoencephalopathy Monitoring Phase**

Safety Objective	Corresponding Endpoint

 
Post-trial safety surveillance with focus on PML monitoring in patients who have stopped treatment
 
	
 
Occurrence of confirmed PML events
 

PML=progressive multifocal leukoencephalopathy.

### **3. STUDY DESIGN**

#### **3.1 DESCRIPTION OF THE STUDY**

This pediatric PK/PD study consists of multiple phases. The randomized treatment phase is an open-label, randomized phase in which etrolizumab is administered to patients on the basis of body weight (mg/kg); randomization will be stratified by weight (<40 kg, ≥40 kg). Patients will be randomized in a 1:1 ratio to receive either high-frequency etrolizumab once every 4 weeks (Q4W) or low-frequency etrolizumab once every 8 weeks (Q8W). The high-frequency dose of 1.5 mg/kg etrolizumab will be administered Q4W (Weeks 0, 4, 8, and 12). The low-frequency dose of 3.0 mg/kg etrolizumab will be administered Q8W (Weeks 0 and 8).

After the 24-week randomized treatment phase (which includes a 16-week treatment period and an 8-week safety follow-up period), patients will then have the option to participate in the 312-week OLE phase (treatment with etrolizumab 1.5 mg/kg will be administered Q4W). All patients who participate in the 24-week randomized treatment phase and the 312-week OLE phase *will enter the 12-week safety follow-up period (see Appendix 1d; no etrolizumab treatment) and will complete the safety surveillance PML-monitoring phase (see Appendix 1e; no etrolizumab treatment for a total of 104 weeks)*. All patients who choose not to enter the OLE phase after the 24-week randomized treatment phase will enter the 104-week PML monitoring phase.

Patients can enter the OLE phase after completion of the 24-week randomized treatment phase. If the last visit of the randomized treatment phase and Day 1 of the OLE phase occur on the same day, the assessments from the randomized treatment phase should be completed. The assessments from the randomized treatment phase can apply to the OLE assessments (i.e., the same assessments should not be repeated for the OLE).

The 104-week PML monitoring phase will consist of telephone calls approximately every 6 months (see [Appendix 7](#)) with administration of the PML Subjective Checklist. If there are any signs or symptoms suggestive of PML identified on this subjective checklist during the telephone call, the patient will be asked to come into the clinic for a neurologic examination. The PML Algorithm (see [Appendix 8](#)) will be followed for any suspected

case of PML, and any confirmed case of PML will be reported as a serious adverse event (see Section 5.4.2).

Patients who experience clinically significant worsening in their UC or CD status during the study can receive rescue therapy based on current standard of care. Patients can receive rescue therapy at any time during the study, including the treatment phase, safety follow-up phase, OLE phase and PML monitoring phase.

[figure not shown]
Approximately 24 pediatric patients from 4 to <18 years of age with moderate to severe UC or with moderate to severe CD will be enrolled to target at least 12 patients with evaluable PK profiles. At least 4 patients from 4 years to <12 years of age should be enrolled, which is a study obligation according to the health authority requirement. If PK and PD samples are missing, patients will be replaced at the discretion of the sponsor. Every effort should be made to collect all PK and PD samples.

Patients who initially failed screening may be rescreened twice at the discretion of the investigator.

If a patient fails any laboratory inclusion/exclusion criteria at screening, the investigator may repeat the test twice within the screening period. If the patient fails the laboratory criteria for a third time they will be considered a screen failure. It will not be considered a re-screening if blood samples have to be redrawn due to sample handling problems, breakage, or sample integrity. This multi-center study will be conducted at global sites.

The study design schemas are presented in [Figure 1](#), [Figure 2](#), and [Figure 3](#). A schedule of activities is provided in [Appendix 1](#).

